5.11 King's ALS Clinical Staging System

The King's ALS Clinical Staging System (Roche et al. 2012) is a 4-level ordinal scale with the first three levels indicating the number (1, 2, or 3) of distinct central nervous system regions (bulbar, upper limb, and lower limb) with neuromuscular dysfunction and levels 4a and 4b indicating nutritional or respiratory failure secondary to ALS, respectively.

Participants will be classified to King's stage 1, 2, 3, 4a, or 4b based on scores from ALSFRS-R assessments according to a published derivation (Balendra et al. 2014). Bulbar involvement is defined as a score less than 4 on any of the ALSFRS-R questions in the bulbar domain (questions 1, 2, and 3). Upper limb involvement is defined as a score less than 4 on either of the ALSFRS-R questions related to hand function (questions 4 and 5A). Lower limb involvement is defined as a score less than 4 on the ALSFRS-R question about walking (question 8). Nutritional failure is defined as responding that the participant uses gastrostomy for greater than 50% of their nutrition. Respiratory failure is defined as a score of 0 on the ALSFRS-R question addressing dyspnea (question 10 or R-1) or a score less than 4 on the ALSFRS-R question about use of mechanical ventilation (question 12 or R-3). Participants without evidence by ALSFRS-R scores of involvement of any of the three central nervous system regions will be scored as King's stage 1 due to their confirmed diagnosis with ALS. Participant may meet criteria for both King's stage 4a and 4b.

5.12 Hospitalization and Other Clinical Events

Times to the following clinically relevant events are defined:

- Time to first hospitalization due to a serious adverse event (SAE),
- Time to first hospitalization due to an ALS-related SAE,
- Time to first use of assisted ventilation,

- Time to first placement of a feeding tube,
- Time to King's stage 4a or 4b, and
- Time to first instance of hospitalization for an SAE, feeding tube placement, tracheostomy, initiation of PAV, or death.

Time at risk for each event will be measured from each participant's Baseline Visit. Time to first hospitalization excludes hospitalizations for elective procedures. ALS-related SAEs are those indicated as related to ALS disease progression by the site investigator. Participants who are already using assisted ventilation or have a feeding tube at the time of the Baseline Visit will be excluded from analysis of those endpoints. Death or death equivalent will be considered an outcome for each of the events listed, forming a composite endpoint.

Time at risk for these events will be censored at the Week 24 Visit, if completed, the date of consent withdrawal, if withdrawn, or the last date at which the status of each endpoint is known prior to the end of the Week 24 Visit window for participants lost to follow-up. Time to King's stage 4a or 4b is interval censored between ALSFRS-R assessments.

5.13 Pharmacokinetics of Pridopidine

Plasma samples collected at the Week 4 and Week 24 visits will be analyzed to quantify the concentration of pridopidine. Details of the assay technique will be added once the procedures are confirmed.

6. Statistical Methodology

6.1 Analysis Sets

The ITT analysis set is henceforth referred to as the Full Analysis Set (FAS) and defined as follows:

- Full Analysis Set (FAS): Participants who were randomized within RGD plus placebo participants from specified regimens, classified according to their randomized treatment assignment. Participants who discontinue study drug but remain in the study will be included in the FAS. Observations completed after regimen data lock are excluded. Participants determined to not meet ALS diagnostic criteria are excluded.

The definition of the STF analysis set is revised as follows:

- Safety Full (STF) Set: Participants who initiated treatment within RGD plus placebo participants from specified regimens who are not known to be ineligible for RGD and who initiated treatment in their respective regimen, classified according to the treatment they actually received. Observations made after premature permanent discontinuation of study drug are included in this sample, should such participants remain on study. Observations completed after regimen data lock are excluded.

An analysis set restricting shared placebo participants to those regimens in which study drug is administered by the same route as RGD is defined as follows:

- Efficacy Common Mode of Administration (ECM) Set: The subset of participants in the FAS analysis set who are in regimens in which study drug is administered by the same route as RGD.

The definitions of the ECC, ERO, STN, and SRO analysis sets are the same as described in the M-SAP with reference to the ITT analysis set now referencing the FAS analysis set. The following analysis sets are specific to RGD:

- Modified Intention-to-treat (mITT) Set: Participants who were randomized within RGD plus placebo participants from specified regimens, who received at least one dose of study drug, and who completed at least one post-baseline ALSFRS-R assessment, classified according to their randomized treatment assignment. Participants who discontinue study drug but remain in the study will be included in the mITT. Observations completed after regimen data lock are excluded.
- Efficacy Per-protocol (EPP) Set: The subset of participants in the FAS analysis set who initiated study treatment and who were not involved in protocol deviations related to eligibility, treatment, follow-up, or assessment, classified according to the treatment they actually received. Final specification of participants included vs. excluded from the EPP analysis set will be defined prior to data lock. Inclusion or exclusion from the EPP analysis set of any participant for whom treatment assignment was unblinded prior to data lock will be governed by the prespecified criteria above. If a participant's data is truncated for inclusion in the EPP analysis set due to a time-dependent event, e.g., initiation of a prohibited medication or non-adherence to protocol-specified dosing, clinical events observed up to 28 days after the censoring event will be included in the EPP analysis set. Data from placebo participants shared from other regimens will not be truncated due to non-adherence to protocol-specified dosing.

Applicable analysis sets (FAS, mITT, ECM, EPP, STF, and STN) will include shared placebo participants from regimens A, B, and C. As only concurrently enrolling regimens are contributing to efficacy analyses, the FAS and ECC analysis sets are synonymous in RGD and only the FAS analysis set will be referenced. As regimen A is administered by subcutaneous injection and regimens B and C are administered orally, only regimens B and C will contribute shared placebo participants to the ECM and STN analysis sets.

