3.6 Missing Data

Handling of missing data is the same as described in the M-SAP except as indicated below. Mean imputation of any missing baseline covariates will impute after transformation for any transformed covariates. Clinic-based assessments that are missing due to COVID-19 restrictions or disruptions are considered missing at random.

Handling of missing data depends upon the type and pattern of missing data (monotone, non-monotone, deaths), the endpoint analyzed (ALSFRS-R, SVC, HHD, etc.), the method of analysis (continuous, time to event, responder), and the reason for missing data (related to lack of efficacy, related to tolerability, administrative reasons unrelated to lack of efficacy or tolerability, and unknown reasons).

Deaths are considered a special type of missing data.

For continuous analysis of all endpoints, the method described in the M-SAP for handling missing data will be followed.

For time-to-event analyses that depend on scheduled assessments, participants lacking any post-baseline assessment not due to death or disease progression will be censored at baseline and functionally omitted from the analysis. If data are missing not due to death, no imputation will be made for the primary analysis. As a sensitivity analysis, multiple imputations as described in Section 6.5.10 Placebo Multiple Imputation below will be used. All subjects who die, reach a death equivalent, or early terminate due to disease progression before reaching the pre-specified time-to-event will be considered as having the unfavorable event being analyzed (e.g., worsening by 1 or more points in bulbar subscale score) at the time of death, death equivalent or early termination, respectively.

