6.5 Secondary Efficacy Analyses

6.5.1 Hierarchical Testing

Primary inference for secondary efficacy endpoints will be based on analysis of the FAS analysis set or subsets of the FAS analysis set as defined below. Primary estimates and inference for time-to-event endpoints will be by Kaplan-Meier product-limit estimates and log-rank test (see Section 6.5.6 below). Primary estimates and inference for responder endpoints will be by logistic regression as described in Section 6.5.5 with missing data handled as indicated in Section 3.6. Primary estimates and inference for rate of change of continuous endpoints will be by a random-slopes linear mixed model (see Section 6.5.3 below). The sequence for testing secondary efficacy endpoints is the following:

1. Time to first decline of 2 points or greater post-baseline in the ALSFRS-R total score among participants in FAS with bulbar dysfunction at baseline defined as an ALSFRS-R bulbar domain (Q1-Q3) score of less than 12,

2. Proportion of participants experiencing no worsening in the ALSFRS-R bulbar domain (Q1-Q3) score from baseline through Week 24 among all participants in FAS,
3. Rate of change in respiratory function as measured by slow vital capacity (SVC) maximum percent predicted from baseline through Week 24 among participants in FAS with bulbar dysfunction at baseline defined as an ALSFRS-R bulbar domain (Q1-Q3) score of less than 12,
4. Time to first decline post baseline of 1 point or greater in the ALSFRS-R bulbar domain (Q1-Q3) score among all participants in FAS, and
5. Time to death or death equivalent through Week 24 among all participants in FAS.

If the primary analysis indicates a significant slowing in disease progression from the Bayesian shared-parameter, repeated-measures model of ALSFRS-R and mortality, then each secondary efficacy endpoint in succession would be declared significant in the specified sequence using a comparison-wise criterion of two-tailed $p < 0.05$. After the first failure to declare significance, no endpoints lower in the hierarchy can be significant. This sequential closed-testing procedure controls the overall type 1 error rate at 5%. Nominal comparison-wise p-values for secondary efficacy endpoints will also be reported.

All secondary efficacy analyses specified here for hierarchical testing will also be analyzed in the mITT analysis set as sensitivity analyses.

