6.5.4 Time to First Evidence of Bulbar Dysfunction

The time to first evidence of bulbar dysfunction will be compared between treatments by Kaplan-Meier product-limit estimates and log-rank test in the subset of participants with an ALSFRS-R bulbar domain (Q1-Q3) score of 12 at the Baseline Visit in the FAS, mITT, ERO, and EPP samples. If greater than 10% of participants develop bulbar dysfunction after baseline, treatments will be compared by Cox proportional hazards regression adjusting for time since ALS symptom onset, delta-FRS, use of riluzole at baseline, use of edaravone at baseline, and use of Nuedexta at baseline with a random gamma-distributed regimen-specific frailty term. If convergence is not obtained, then the frailty term will be dropped. A separate supportive analysis will include centered baseline serum NfL level as an additional covariate.

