6.5.6 Survival and Time to Clinical Events

Survival and time to hospitalizations and clinical events will be analyzed in the FAS, mITT, ECM, ERO, EPP, STF, and SRO analysis sets. Survival analyses that include follow-up beyond the placebo-controlled period will be analyzed in the ERO analysis set. The summaries and analyses of time to death or death equivalent are the same as specified in the M-SAP with the addition of baseline age as a covariate in adjusted models, with the addition that the endpoints of time to death independent of occurrence of death equivalents and time to each of the hospitalization and clinical events will be separately analyzed using the same models, and with an additional adjusted analysis that includes baseline serum NfL level as a covariate. Analysis of time to King's stage 4a or 4b will accommodate interval censoring between ALSFRS-R assessments and will be stratified by baseline King's stage.

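### The mITT set drops participants who die, or leave for progression with no ALSFRS-R, before the first assessment, although SAP 3.6 counts them as events or non-responders

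*SAP*

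**What the plan says.** SAP 6.1 defines mITT as randomised participants in the regimen, plus shared placebo participants, "who received at least one dose of study drug, and who completed at least one post-baseline ALSFRS-R assessment". Nothing in the definition provides for someone whose assessment is absent because they died.

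The set is used in three places:

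- SAP 6.5.1 says the five hierarchical secondary analyses "will also be analyzed in the mITT analysis set as sensitivity analyses".
- SAP 6.5.4 compares time to first bulbar dysfunction "in the FAS, mITT, ERO, and EPP samples".
- SAP 6.5.6 states: "Survival and time to hospitalizations and clinical events will be analyzed in the FAS, mITT, ECM, ERO, EPP, STF, and SRO analysis sets".

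SAP 3.6 takes the opposite line on the same people. In assessment-based time-to-event analyses, a participant with no post-baseline assessment is functionally omitted only if the reason is neither death nor progression. "All subjects who die, reach a death equivalent, or early terminate due to disease progression" before the event of interest are given that event. For responder endpoints the same three groups are non-responders.

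Confirmatory inference lies elsewhere. SAP 6.5.1 says: "Primary inference for secondary efficacy endpoints will be based on analysis of the FAS analysis set or subsets of the FAS analysis set". The FAS has no post-baseline requirement. It does carry one exclusion that the mITT definition lacks: "Participants determined to not meet ALS diagnostic criteria are excluded".

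**The concern.** Having a post-baseline ALSFRS-R is itself an outcome after randomisation. A participant who dies in the first weeks cannot have one, so the rule removes some of the worst outcomes and keeps everyone who reached an assessment. SAP 5.10 starts survival time at the Baseline Visit. In mITT, the weeks up to the first assessment therefore count as time at risk for people selected partly for having got through them.

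If early deaths were unevenly spread between arms, the arm with more of them would look better in mITT than in the FAS. A sensitivity analysis that loses these events is a poor check on the FAS result. The plan is more careful in its per-protocol set (SAP 6.1), which keeps clinical events for up to 28 days after a participant's data are truncated.

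A smaller drafting gap adds to this. The ECM and EPP sets are defined as subsets of the FAS, but mITT is not. Read literally, it can hold participants whom the FAS excludes for not having ALS, so a difference between mITT and FAS could mix two causes.

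**Working it through.** **Step 1: the rules side by side, for a dosed participant who dies before any post-baseline ALSFRS-R.**

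| Hierarchical endpoint (SAP 6.5.1) | Treatment in the FAS | In mITT |
|---|---|---|
| 1. Time to ALSFRS-R decline of 2 or more points, bulbar dysfunction at baseline | Event at death (3.6) | Absent; event lost |
| 2. No bulbar worsening to Week 24 | Non-responder (3.6) | Absent; non-response lost |
| 3. SVC slope, bulbar dysfunction at baseline | No death-as-event rule; missing at random, no imputation (6.5.3) | Absent; no event to lose |
| 4. Time to bulbar decline of 1 or more points | Event at death (3.6) | Absent; event lost |
| 5. Death or death equivalent | Event, timed from the Baseline Visit (5.10) | Absent; event lost |

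Time to bulbar dysfunction behaves like endpoint 4. The clinical-event times behave like endpoint 5, because SAP 5.12 counts death or death equivalent as an outcome for each.

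**Step 2: who is actually removed.** The Early Termination Visit repeats the Week 24 assessments (protocol 6.1.10), and these include ALSFRS-R (SAP 2.9). A participant who stops for progression and attends that visit with an ALSFRS-R stays in mITT. So does someone who reaches a death equivalent and later completes an ALSFRS-R. The loss is confined to deaths before any ALSFRS-R and to exits with no ALSFRS-R at all.

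**Step 3: size.** The documents give no event or power figure on this point to reproduce. Protocol 9.4 says only that event rates are expected to be low.

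Inputs from the documents:
- about 160 participants at 3:1, which gives 160 × 0.75 = 120 active and 160 × 0.25 = 40 placebo;
- first post-baseline ALSFRS-R at day 28 ± 7 (SAP 2.9);
- Week 24 at day 168.

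Assumptions: constant hazard, and a 24-week risk r of death or death equivalent of 2%, 5% or 10%.

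Daily hazard h = −ln(1 − r)/168. Probability of an event before day d: q = 1 − exp(−h·d).

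| r | q at day 28 | Share of 24-week events, q/r | Expected of 160 | Chance of at least one in 160 |
|---|---|---|---|---|
| 2% | 0.34% | 16.8% | 0.54 | 42% |
| 5% | 0.85% | 17.0% | 1.36 | 75% |
| 10% | 1.74% | 17.4% | 2.79 | 94% |

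Over the visit window (days 21 to 35) the share runs from 12.6% to 21.7%, and the expected number of 160 from 0.40 to 3.47. The share is close to 28/168 = 16.7% whatever r is, so it mainly restates the constant-hazard assumption. The counts are an upper bound for the death and death-equivalent component, because of the retained death equivalents in step 2. Exits for progression with no ALSFRS-R would add to the loss, but no rate is given for them.

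**Step 4: what a few lost events could do.** Assume 6 events among 120 active participants (5.0%) against 5% on placebo, a risk ratio of 1.00. Remove early events from the active arm only, as an extreme case:

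- one removed: 5/119 = 4.2%, ratio 0.84;
- two removed: 4/118 = 3.4%, ratio 0.68;
- three removed: 3/117 = 2.6%, ratio 0.51.

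At r = 5% the expected number before day 28 in the active arm is 120 × 0.0085 = 1.02, so the first line is the typical size and the other two are less likely.

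**The case against.** The strongest reply is that nothing is decided on mITT. A reader might infer that early deaths are lost from the confirmatory hierarchy. The documents do not support that: primary inference is in the FAS, where these people count. Survival is also reported in six sets besides mITT, so a distorted mITT result would stand beside others. This stands, and it limits the point to sensitivity analyses.

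A reader might also infer that every early progression exit or death equivalent disappears. The Early Termination Visit and continued follow-up after a death equivalent rule that out. Nor does the one-in-six share carry over to the whole hierarchy. It applies to death or death equivalent; endpoints 1, 2 and 4 also count functional decline, and endpoint 3 loses no event.

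Distortion of the comparison needs an imbalance between arms, and nothing in the documents predicts one. The number of shared placebo participants from regimens A to C is not stated, so no count beyond the 160 can be given.

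On the diagnosis exclusion, the hierarchical endpoints are worded in terms of FAS participants, so it can be read as carried over into mITT. That is reasonable, but it is an inference that the set definition could make unnecessary.

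These replies shrink the point without removing it. No part of the SAP returns a death before the first ALSFRS-R to mITT. The Master SAP was not available for this review, but SAP 6.1 presents mITT as specific to this regimen and SAP 1 ranks this plan above the Master SAP.

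**Conclusion.** The point holds for the mITT sensitivity analyses of hierarchical endpoints 1, 2, 4 and 5, and for the mITT analyses of time to bulbar dysfunction, survival and clinical events. In these the set definition overrides the event and non-response rules for participants who die, or leave for progression with no ALSFRS-R, before the first assessment. The confirmatory FAS results are not affected.

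Under a constant hazard and an assumed 24-week risk of 2% to 10%, about 17% of deaths or death equivalents fall before day 28 (13% to 22% over days 21 to 35). That is at most about 0.5 to 2.8 of the 160 regimen participants at day 28. The number is small, but the survival endpoint is expected to have few events. The direction and size of any effect on the treatment comparison depend on an imbalance that the documents do not let one estimate. It is a cheap improvement, not a threat to the main conclusions.

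**What to change.** Define mITT in SAP 6.1 as the subset of the FAS who received at least one dose and who have either a post-baseline ALSFRS-R assessment or, before any such assessment, a death, death equivalent or early termination for disease progression. The subset wording also carries over the ALS-diagnosis exclusion and brings mITT into line with ECM and EPP.

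The cost is one clause, with no new data and no change to the confirmatory tests. There is a small downside. SAP 3.6 already omits, in effect, participants with no post-baseline assessment for other reasons from the assessment-based time-to-event analyses. For those endpoints the revised mITT will be close to the dosed FAS and will add little as a separate check.

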6.2 Baseline Characterization

The baseline characteristics summarized for participants randomized within RGD are the same as specified in the M-SAP with the addition of ALSAQ-40 domain scores and SI, CNS-BFS total score, CNS-LS score, King's stage, weight, body mass index (BMI), serum urate concentration, serum creatinine concentration, serum NfL concentration, and baseline use of Nuedexta.

6.3 Primary Efficacy Analysis and Supportive Analyses

The primary analysis for RGD is a Bayesian shared-parameter, repeated-measures model of ALSFRS-R that accounts for loss of follow-up due to mortality. Details of the model, including documentation of operating characteristics under a range of scenarios, are provided in the "ALS Master Protocol Recommended Statistical Analysis, Design and Simulation Report" (Appendix 1 to the Master Protocol). The Bayesian shared-parameter, repeated-measures model will be

applied to the FAS analysis set as the primary analysis, to the ECM and ERO analysis sets as sensitivity analyses, and to the EPP analysis set as a supportive analysis.

The estimand of the primary analysis is the relative rate of disease progression (the "disease rate ratio" or DRR) of active treatment relative to placebo in the FAS population under an assumption that active treatment slows mean time to death or death equivalent by the same proportion as treatment slows the mean rate of functional progression as measured by change in ALSFRS-R total score over time. The estimand is defined by the following attributes:

- Treatment: pridopidine administered orally at a dosage of 45 mg BID vs. placebo.
- Population: FAS population as defined in Section 6.1.
- Variables: time to death or death equivalent and rate of change in ALSFRS-R total score from baseline to the Week 24 Visit.
- Intercurrent event 1: treatment discontinuation due to death or death equivalent: no ALSFRS-R data from participants who reach the death or death equivalent endpoint are included in the analysis, handled via mortality component in model, composite variable strategy approach.
- Intercurrent event 2: treatment discontinuation not due to death or death equivalent: handled via treatment policy approach, all data will be used including data collected during the placebo-controlled period after treatment discontinuation regardless of concomitant medication, for those participants who have not been censored due to mortality. Missing data post-treatment will not be imputed, handled via missing at random assumption.
- Population-level summary: mean ratio of hazard or progression rate of active treatment relative to placebo.

